9.1.3 Lost to follow-up

For patients whose status is unclear because they fail to appear for study visits without stating an intention to discontinue from study treatment or discontinue from study or withdraw consent/oppose to the use of their data/biological samples, the investigator should show "due diligence" by contacting the patient, family or family physician as agreed in the informed consent and by documenting in the source documents steps taken to contact the patient, e.g. dates of telephone calls, registered letters, etc.

A patient should not be considered lost to follow-up until due diligence has been completed. Patients lost to follow up should be recorded as such on the appropriate Disposition CRF.

9.1.4 Early study termination by the sponsor

The study can be terminated by Novartis at any time based on the occurrence of any of the following:

- Unexpected, significant, or unacceptable safety risk to subjects enrolled in the study.

- Decision based on recommendations from applicable board(s) after review of safety and efficacy data
- Discontinuation of study drug development.

In taking the decision to terminate, Novartis will always consider subject welfare and safety. Should early termination be necessary, the patient must be seen as soon as possible and be treated as a patient who discontinued from study treatment. The same assessments should be performed as described in [Section 9.1.1](#) for a discontinued or withdrawn patient. The Investigator may be informed of additional procedures to be followed in order to ensure that adequate consideration is given to the protection of the patient's interests. The Investigator or sponsor, depending on local regulation, will be responsible for informing IRBs and/or ECs of the early termination of the trial.

9.1.5 Follow up for safety evaluations

1. Safety Follow-up Visit

All patients must have a follow-up visit for safety evaluations 30 days (+ 3 day visit window) following the last dose of study treatment based on discontinuation from Treatment Period.

At the Safety Follow-Up visit, adverse events and therapies after treatment discontinuation will be reviewed. In addition, serum pregnancy will be collected for female patients of child-bearing potential. Refer to [Table 8-1](#). Patients who remain on ruxolitinib at Week 48 and obtain access to ruxolitinib outside of the study will not complete the safety follow-up visit since study treatment will continue.

1. Long-term safety Follow-up

All patients who discontinue study treatment (responders, non-responders, completing or prematurely discontinued from treatment period for any reasons as outlined above) will enter in the Long Term Follow-Up period, which lasts up to 24 months from start of study treatment (Day 1). Patients who prematurely discontinue ruxolitinib prior to Week 24 (without achieving CR or PR), must have assessments performed at the end of Week 24 ([Table 8-1](#)) and subsequently enter the Long Term follow-up period.

Visits are scheduled every six months (+/- 1 month from scheduled visit) starting Month 12 followed by subsequent visits at Month 18 and Month 24. Patients who may have an End of Treatment at Week 48 due to extended taper or aGvHD flare, will have the long-term follow up at Month 18 and 24 only.

Information to be collected during Long-Term follow-up is detailed in [Table 8-1](#). Data collected should be entered in the appropriate eCRF. Unscheduled visits may be performed as necessary. Additional assessments may be done as per institutional guidelines at investigator's discretion at any time during the trial.

9.2 Study completion and post-study treatment

End of Study (EoS) will occur when all patients have reached Month 24 (i.e., the end of the long term follow-up observation period), unless the patient discontinues earlier.

The final analysis will occur once all patients have completed the Long Term Follow-Up period to 24 months. All available data from all patients up to EoS, inclusive of OS, will be reported in a final Clinical Study Report (CSR).

Patients who meet the protocol criteria for treatment discontinuation will not be eligible to continue receiving ruxolitinib within the study.

However, where permitted by and in accordance to local laws and regulations, and as part of Novartis “Post-trial access” commitment, **patients who meet all of the following criteria may be given the possibility to continue ruxolitinib outside the study, if requested:**

1. Responded (CR or PR; Refer to [Table 8-3](#)) to ruxolitinib at Day 28
2. Did not meet study discontinuation criteria ([Section 9.1.1](#))
3. Are assessed by the Investigator to still be deriving clinical benefit from ruxolitinib,

may be given the possibility to continue ruxolitinib outside the study, if requested.

Subjects who have not completed ruxolitinib tapering at the end of their study treatment period (Week 48) and are still deriving clinical benefit from ruxolitinib as assessed by the Investigator, may be considered to have completed the study and may be given the possibility to continue ruxolitinib outside of the study. If a patient meets the criteria for post-trial access, the Investigator may consider a ruxolitinib formulation change upon completion of CINC424F12201 and upon enrollment into post-trial access.

10 Safety monitoring reporting and committees

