All patients will be enrolled and treated for 24 weeks (approximately 6 months) or until early discontinuation. All patients will also be followed for additional 18 months (total duration = 2 years from enrollment). Should the occurrence of aGvHD flare require treatment re-initiation or should ruxolitinib not be discontinued by the end of 24 weeks due to extended tapering, patients may continue taper ruxolitinib beyond 24 weeks up to a maximum of 48 weeks. As patients ≥ 12 y to < 18 y (Group 1) are already being included in [[CINC424C2301]], and treated with 10 mg BID, this dose is the recommended phase II dose (RP2D), and will be used to treat all patients in this age group. For the Ph II, all other age groups will be treated with the RP2D determined during the Ph I. Therefore, all ≥ 12 to < 18 year old patients will automatically be enrolled in Phase II. It is planned that the first 5 patients treated in Group 1 will undergo extensive PK sampling to inform the RP2D determination of the younger age groups in the Ph I. Additional patients may undergo extensive sampling should one or more of the first 5 patients not be evaluable or until the dose/exposure is confirmed.

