3.3 Study periods

The study is comprised of the following periods:

- **Screening Period (Day -28 to Day -1)**

Patients diagnosed with treatment-naïve or steroid refractory aGvHD will have screening activities and assessment of inclusion and exclusion criteria once the study informed consent is obtained. Upon confirmation of eligibility, the patients will be enrolled to the study.

- **Treatment Period (Day 1 to Week 24)**

Study treatment will begin on Day 1. Subjects meeting eligibility requirements will be treated with ruxolitinib plus corticosteroids +/- CNI for 24 weeks (approximately 6 months) unless discontinuation criteria (See [Section 9.1.1](#)) or withdrawal from the study for other reasons occurs. Dose modifications are allowed for safety. Patients that have not discontinued ruxolitinib by the end of Week 24 or experience aGvHD flare may continue to receive treatment for a maximum of 48 weeks (See [Section 6](#) for treatment details and dose modifications). In this case, the end of treatment for such patients will extend beyond Week 24 but MUST end by Week 48.

Study visits will occur per the following schedule to monitor tolerability and efficacy of the study treatments during the Treatment period:

- Weekly visits from Day 1 up to Day 56;
- Visits every 4 weeks beyond Day 56 and until Week 24 or End of Treatment (EOT), whichever occurs later.

A 30-day safety follow-up visit will be done for all patients after the last dose of ruxolitinib.

- **Long-term follow-up Period (From EOT to Month 24)**

[figure not shown]
Recognizing that aGvHD is a complication of alloSCT that often leads to death within 2 years after the procedure, and that assessment of long-term safety and durable efficacy is clinically meaningful, all patients (responders and non-responders in both arms, regardless of when treatment was discontinued) will be followed to collect long term data including: survival, any relapse/progression of the underlying hematologic disease for which the alloSCT procedure was performed (refer to [Section 16.3](#) Appendix 3), NRM, any occurrence of graft failure, EFS, any occurrence of cGvHD, and occurrence of any second primary malignancies.

Visits will be performed at 12, 18, and 24 months from the start of treatment (Day 1).

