In the event that any patient permanently discontinues the study treatment, regardless of reason, reasonable efforts should be made to have the patient return for an early termination visit and have the End of Treatment evaluations completed as described in [Section 8](#). All patients completing/discontinuing study treatment at any time point will be followed in the Long-term follow-up period until they reach 2 years from Day 1.

The date any patient discontinued the study treatment and the specific reason for discontinuation will be recorded in the eCRF.

Table 6-3 Criteria for interruption and re-initiation of ruxolitinib treatment for adverse events suspected to be drug-related

Dose modifications for ruxolitinib for adverse events suspected to be drug-related	
Worst toxicity	
Investigations (Hematologic)	
Neutropenia (ANC)	
Grade 1 (ANC < LLN - 1500/mm3)	Recommendation: Maintain dose level
Grade 2 (ANC < 1500 - 1000/mm3)	Recommendation: Maintain dose level
Grade 3 (ANC < 1000 - 750/mm3)	Recommendation: Maintain dose level
Grade 3 (ANC < 750 - 500/mm3)	Mandatory: Reduce 1 dose level (see Table 6-4), monitor ANC daily until resolved to ≤ Grade 2, then resume initial dose level
Grade 4 (ANC < 500/mm3)	Mandatory: Hold dose, monitor ANC daily until resolved to ≤ Grade 3, then resume at reduced 1 dose level (Table 6-4). If resolves to ≤ Grade 2, can resume initial dose level. If not resolved in ≤14 days the patient must be discontinued.
Febrile neutropenia (ANC < 750/mm3, fever ≥ 38.5°C)	Mandatory: Hold dose until resolved, then restart at reduced 1 dose level
Thrombocytopenia	
Grade 1 (PLT < LLN-75,000/mm3)	Recommendation: Maintain dose level
Grade 2 (PLT < 75,000 - 50,000/mm3)	Recommendation: Maintain dose level
Grade 3 (PLT < 50,000 - 25,000/mm3)	Recommendation: Maintain dose level
Grade 4 (PLT < 25,000 - 20,000/mm3)	Recommendation: Maintain dose level
Grade 4 (PLT < 20,000 - 15,000/mm3)	Mandatory: Reduce 1 dose level until resolved to ≥20,000/mm3 If resolved in ≤ 7 days, then resume initial dose level If resolved in > 7 days, then maintain at reduced 1 dose level

Dose modifications for ruxolitinib for adverse events suspected to be drug-related	
Worst toxicity	
Grade 4 (PLT < 15,000/mm ³)	Mandatory: Hold dose until resolved to $\geq 20,000/\text{mm}^3$, then resume at reduced 1 dose level. If resolves to \leq Grade 3, can resume initial dose level. If not resolved in ≤ 14 days the patient must be discontinued.
Investigations (Renal)	
Serum creatinine	

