11.4 Data Confidentiality

Information about study subjects will be kept confidential and managed under the applicable laws and regulations. Those regulations require a signed subject authorization informing the subject of the following:

1. What protected health information (PHI) will be collected from subjects in this study?
2. Who will have access to that information and why?
3. Who will use or disclose that information?
4. The rights of a research subject to revoke their authorization for use of their PHI.

In the event that a subject revokes authorization to collect or use PHI, the investigator, by regulation, retains the ability to use all information collected prior to the revocation of subject authorization. For subjects that have revoked authorization to collect or use PHI, attempts should be made to obtain permission to collect follow-up safety information (e.g. has the subject experienced any new or worsened AEs) at the end of their scheduled study period.

The data collection system for this study uses built-in security features to encrypt all data for transmission in both directions, preventing unauthorized access to confidential patient information. Access to the system will be controlled by a sequence of individually assigned user identification codes and passwords, made available only to authorized personnel who have completed prerequisite training.

12 Data analysis and statistical methods

The final analysis will be conducted and the clinical study report (CSR) written once all patients have completed the study (i.e. completed the long-term follow-up period of Month 24) or discontinued earlier. Analysis cut-off date will be defined corresponding to the analysis time point and all data captured in the study up to that cut-off will be reported. Any data analysis carried out independently by the investigator should be submitted to Novartis before publication or presentation.

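### Protocol 9.2 lets a child still tapering ruxolitinib at Week 48 be treated as having completed the study, which conflicts with follow-up to Month 24 and could cost that child's Month 18 and 24 data (minor)

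*Protocol*

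**What the plan says.** Protocol 9.2 deals with children who have not finished tapering ruxolitinib when study treatment ends at Week 48 and who still benefit from it. Such a child "may be considered to have completed the study and may be given the possibility to continue ruxolitinib outside of the study". The next sentence allows a formulation change "upon completion of CINC424F12201 and upon enrollment into post-trial access", so it places leaving the study and entering post-trial access at the same moment.

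The same section also states that "End of Study (EoS) will occur when all patients have reached Month 24". The opening of Protocol section 12 explains that the final analysis waits until patients have "completed the study (i.e. completed the long-term follow-up period of Month 24"). Section 3 plans that "All patients will also be followed for additional 18 months (total duration = 2 years from enrollment"). Section 3.3 follows all patients "regardless of when treatment was discontinued". For those with a prolonged taper it says that "the end of treatment for such patients will extend beyond Week 24 but MUST end by Week 48". Section 6.5.2.1.2 adds that "All patients completing/discontinuing study treatment at any time point will be followed in the Long-term follow-up period", to two years from Day 1.

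Section 9.1.5 gives patients whose treatment ends at Week 48 because of an extended taper or flare their long-term visits at Months 18 and 24 only. For patients who obtain ruxolitinib outside the study at Week 48, it waives the 30-day safety visit, on the ground that study treatment goes on.

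**The concern.** The protocol uses two meanings of completion. One is reached at Month 24. The other may be applied at Week 48 to children who move to post-trial access. A site that takes the second literally can stop visits for these children and record them as completers.

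These children have the longest ruxolitinib exposure in the trial. The visits at risk carry survival, relapse or progression, graft failure, chronic GvHD, second malignancy, height and weight. SAP 3.7.1 would censor OS, EFS, NRM and cGvHD incidence at last contact, before the 18- and 24-month estimates of SAP 3.7.2. Protocol 6.1.5.1 links a taper beyond Week 24 to a flare or other safety concern, so the censoring could be informative, in a direction that cannot be known in advance. The disposition summary in SAP 3.3.1 counts patients who discontinued the study, and a child labelled a completer at Week 48 would not appear there.

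**Working it through.** The plan gives no figure for this point: neither the number expected to enter post-trial access nor a precision target for the 24-month estimates. Its one efficacy sample-size figure (33 of 45 responders, exact 90% CI 0.604 to 0.838, probability 0.901) reproduces at 0.9005, but nothing here depends on it.

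**Does the text retain these children?**
- For retention: sections 3, 3.3 and 6.5.2.1.2 cover all patients to two years. Section 9.1.1 item 10 makes not being weaned by Week 48 a required discontinuation of study treatment, and 9.1.1 then sends such patients to long-term follow-up as not withdrawn. Section 9.1.5 schedules Months 18 and 24 when treatment ends at Week 48 after an extended taper. Section 8.5.4.8 monitors second malignancies to 24 months.
- Against: 9.2 is the section on study completion, and it permits completion at Week 48. Section 9.1.5 words entry to long-term follow-up for patients who discontinue study treatment, but says of post-trial-access patients that study treatment goes on. Section 9.2 also requires that no 9.1.1 discontinuation criterion was met, although being unweaned at Week 48 is itself such a criterion. A site can therefore be unsure whether the child is a discontinuer, and retained, or a completer.

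The group is retained by category, but no sentence retains it by name.

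**What one closed-out child loses**
- Week 48 is 48 × 7 = Day 336. Month 24 is Day 730 (SAP 3.1.1).
- Last contact at Day 336: 730 − 336 = 394 days, 394/730 = 54%, 394/30.4375 = 12.9 months.
- If the 30-day adverse-event duty in Protocol 10.1.1 carries contact to Day 366: 730 − 366 = 364 days, 50%, 12.0 months.
- With the ±7-day visit window (Protocol 8.3), Week 48 falls on Day 329 to 343. The range is 730 − 329 = 401 days down to 730 − (343 + 30) = 357 days, or 55% to 49%.
- Table 8-1 schedules seven items at each of Months 18 and 24 (height, weight, cGvHD, relapse or progression, second malignancy, graft failure, survival): 7 × 2 = 14 assessments. As 9.1.5 gives this group no Month 12 visit, these are its only remaining scheduled visits.

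**Effect on 24-month OS, by assumption**

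Take 45 patients, N alive at Day 336, d later deaths, k children closed out, and no other censoring.
- If all k die unseen (and are among the d), the Kaplan-Meier estimate is raised by (N − d)k / [45(N − k)], at most k/45. For k = 1, 2, 3 that is 2.2, 4.4 and 6.7 points. With N = 30 and d = 3 it is 2.1, 4.3 and 6.7.
- If all k survive, the estimate falls. With N = 30 and d = 3 the change is −0.2 points for k = 1 and −0.7 for k = 3.
- For scale, the 95% half-width 1.96 × √[p(1 − p)/45] is 11.7 points at p = 0.8 and 14.6 at p = 0.5.

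**The case against.** The strongest reply is that the protocol already answers the question. Section 9.2 itself treats Week 48 as the end of study treatment for these children. Section 9.1.5 gives patients who end there their Month 18 and 24 visits, and where it does name post-trial-access patients it excuses only the 30-day visit. The disputed sentence may exist merely to keep drug access open for children whom 9.1.1 item 10 would otherwise exclude. On this view data are lost only if a site overrides several general rules on the strength of one permissive sentence.

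Most of this stands, and it rules out three stronger readings.
- A reader might infer that nothing in the protocol keeps these children in. That is not so: they are kept in by category.
- A reader might infer that the plan intends to drop them, or that data have been lost. The text only permits completion at Week 48, and the number affected may be zero.
- A reader might infer that the loss would be invisible or would seriously bias survival. Censoring near Days 336 to 366 could still be shown on the Kaplan-Meier output. The 2.2 to 6.7 point shift needs every released child to die unseen, which is unlikely because post-trial access requires a Day 28 response and continuing benefit.

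What does not fall is the conflict itself. The permission is written in the section that governs completion, and the one sentence naming the group rests on treatment continuing.

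**Conclusion.** The conflict is real and the point is minor. Section 9.2 allows a completion status at Week 48 that contradicts Month 24 completion in the same section and in section 12, and nothing expressly says that children in post-trial access remain in follow-up. The consequence is possible, not planned: about half of the two-year follow-up and both remaining visits for each child closed out, with censoring before the 18- and 24-month secondary estimates.

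The day counts assume that last contact is the Week 48 visit or the end of the 30-day adverse-event period. The survival shifts rest on assumed counts of one to three children and on extreme outcomes. No effect on the 12-month estimates is claimed, because last contact may reach about Day 366. Day 28 ORR and durable ORR at Day 56 are unaffected.

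**What to change.** In 9.2, replace the permission to regard the child as a study completer with: *have completed study treatment and remain in long-term follow-up for the Month 18 and Month 24 assessments*. In 9.1.5, add that long-term follow-up includes patients moving to post-trial access. In the CSR, report how many moved at Week 48 and whether Month 18 and 24 data were obtained, and flag data collected on ruxolitinib supplied outside the study.

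The cost is two sentences, one CSR line and two visits that 9.1.5 already schedules. The downside is that centres keep seeing a few children whose drug comes from elsewhere, and their later data reflect that supply.

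Timing limits the reach. This protocol version cites a template dated 14-Jan-2022, and enrollment of 45 was complete as of 11-Feb-2021. Taking enrollment dates for Day 1, both visits were then still ahead for at least the 45 − 30 = 15 patients enrolled after 14-Oct-2020 (at most 457 days in, against Day 546 for Month 18). After about 11-Feb-2023 (11-Feb-2021 plus 730 days) only the CSR line remains useful.

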10.1 Definition of adverse events and reporting requirements

10.1.1 Adverse events

An adverse event is defined as the appearance of (or worsening of any pre-existing) undesirable sign(s), symptom(s), or medical condition(s) that occur after patient’s signed informed consent has been obtained.

Abnormal laboratory values or test results occurring after informed consent constitute adverse events only if they induce clinical signs or symptoms, are considered clinically significant, require therapy (e.g., hematologic abnormality that requires transfusion or hematological stem cell support), or require changes in study medication(s).

Adverse events that begin or worsen after informed consent should be recorded in the Adverse Events eCRF. Conditions that were already present at the time of informed consent should be recorded in the Medical History page of the patient’s eCRF. Adverse event monitoring should be continued for at least 30 days following the last dose of study treatment. Adverse events (including lab abnormalities that constitute AEs) should be described using a diagnosis whenever possible, rather than individual underlying signs and symptoms. When a clear diagnosis cannot be identified, each sign or symptom should be reported as a separate Adverse Event.

Adverse events will be assessed and graded according to the Common Terminology Criteria for Adverse Events (CTCAE) version 4.03.

If CTCAE grading does not exist for an adverse event, the severity of mild, moderate, severe, and life-threatening, death related to the AE corresponding respectively to Grades 1 - 5, will be used. Information about any deaths (related to an Adverse Event or not) will also be collected through a Death form.

The occurrence of adverse events should be sought by non-directive questioning of the patient (subject) during the screening process after signing informed consent and at each visit during the study. Adverse events also may be detected when they are volunteered by the patient (subject) during the screening process or between visits, or through physical examination, laboratory test, or other assessments. As far as possible, each adverse event should be evaluated to determine:

1. The severity grade (CTCAE Grade 1-5)
2. Its duration (Start and end dates)
3. Its relationship to the study treatment (related / not related)
4. Action taken with respect to study treatment (dose increased, dose not changed, dose reduced, drug interrupted, drug withdrawn, not applicable, unknown)
5. Whether Concomitant or additional treatment given due to this adverse event (yes / no)
6. Whether it is serious, where a serious adverse event (SAE) is defined as in [Section 10.1.2](#) and which seriousness criteria have been met

If the event worsens the event should be reported a second time in the eCRF noting the start date when the event worsens in toxicity. For grade 3 and 4 adverse events only, if improvement to a lower grade is determined a new entry for this event should be reported in the eCRF noting the start date when the event improved from having been Grade 3 or Grade 4.

All adverse events should be treated appropriately. If a concomitant medication or non-drug therapy is given, this action should be recorded on the Adverse Event eCRF.

Once an adverse event is detected, it should be followed until its resolution or until it is judged to be permanent, and assessment should be made at each visit (or more frequently, if necessary) of any changes in severity, the suspected relationship to the study treatment, the interventions required to treat it, and the outcome.

The following events, which are components of study endpoints: worsening of study indication (aGvHD) including occurrence of aGvHD flare as defined in [Section 6.1.5.1.1](#), occurrence of chronic GvHD, or progression/relapse of underlying hematologic disease (including fatal outcomes) as defined in [Section 16.3](#) (Appendix 3), should not be reported as a serious adverse event and will be reported on specific CRFs other than AE eCRF.

Adverse events separate from the events listed above (example, deep vein thrombosis at the time of progression or hemoptysis concurrent with finding of disease progression) will be reported as per usual guidelines used for such events with proper attribution regarding relatedness to the drug.

